### **8.2.3 Premature Subject Withdrawal**

All subjects are free to withdraw from participation in the study at any time, for any reason, specified or unspecified, and without prejudice to further treatment. The criteria for enrollment are to be followed explicitly and if a subject who does not meet enrollment criteria is inadvertently enrolled, that subject should be withdrawn from the study and the Sponsor or CRO must be notified.

Subjects should not be asked to withdraw from the study because of experiencing AE, lack of efficacy, pregnancy, or lack of compliance to the clinical study protocol, etc. Those patients can stop their study treatments (for subjects who do not comply the protocol specified instructions and procedures, every effort will be made to keep them in the study after stopping treatment unless there is an adverse impact on subject safety). Discontinuation from study treatment does not automatically lead to a complete withdrawal from the study. Subjects discontinuing from study treatment are strongly encouraged to continue in the study up to the study completion (Follow-up Phone Visit, Week 13).

Subjects who decide they do not wish to remain in the study should NOT be considered withdrawn from the study UNLESS they withdraw their consent. Subjects are encouraged to return to all scheduled site and telephone visits, perform all procedures (including eDiary completion and blood draws) and follow the all requirements of the protocol (including the prohibited therapies), but without study treatment administration, until the end of the study (Follow-up Phone Visit, Week 13).

The reason for study treatment discontinuation and withdrawal from the study will be separately recorded. When the subject discontinues study treatment and/or withdraw from the study, the reason will be recorded in the medical records and eCRF using the below categories for discontinuation of study treatment and withdrawal from the study respectively.

The reasons will be grouped into three main categories: “study treatment related”, “not study treatment related”, and “uncertain” and more specific sub-categories will be described under each of the three main categories.

- Study treatment related
  - Lack of efficacy
  - Adverse events
  - Deviation from protocol (Please specify the deviation)
  - Other
- Not study treatment related
  - Adverse events
  - Prohibited Medication Use
  - Pregnancy
  - Deviation from protocol (Please specify the deviation)
  - COVID-19

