**At home, subjects are required to conduct the following assessments/procedures:**

Perform the following assessments and record in the eDiary on daily basis:

Assess and record the pain of the target knee using the NRS 11-point pain scale when subjects take a shower or bath during the Screening Phase (Approximately every 24 hours. Even if subjects do not take a shower or bath, the assessment is necessary every 24 hours).

Note: If subjects withdraw or discontinue after signing the informed consent and prior to the registration in IWRS, the date and reason will be recorded in IWRS. Detailed information will be provided in a separate Manual.

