**At home, subjects are required to conduct the following assessments/procedures:**

1. Remove the patch before showering/bathing and apply a new patch on the target knee (inner or outer by [REDACTED] rotation) approximately every [REDACTED]  
[REDACTED]
2. Perform the following assessments and record in the eDiary on daily basis:
  - a. Record patient eDiary information [REDACTED] when subjects replace the patch and before they sleep.

- b. Perform and record scoring of the pain of the target knee using the NRS 11-point pain scale when subjects replace the patch. The time of NRS assessment will be recorded in the eDiary. In addition to the regular assessment of NRS, the NRS assessment will be performed immediately before the subject takes any rescue medication on the day (if applicable).
- c. Record the time of patch application and removal when subjects replace the patch.
- d. Record the time of unscheduled complete patch detachment and the reason (if applicable) at the time of unscheduled detachment or before they sleep.
- e. Record the number of tablets of rescue medication used, the time and the reason (if applicable) when subjects take a tablet or before they sleep.
- f. Answer the questionnaires related to adhesion, skin irritation and discomfort when subjects replace a patch and record any issues with adhesion, skin irritation and discomfort.

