#### **13.4.3.3 Analyses for Secondary Endpoints**

All WOMAC LK3.1 OA Indices, PGA, PGIC, and NRS secondary efficacy endpoints will be analyzed similar to the primary analyses. An MMRM model will be used with change from baseline as the repeated dependent variable, with treatment (HP-5000 and placebo), visit, treatment-by-visit interaction, and the baseline assessment score as covariates.

The observed value and change from baseline each assessment score will also be summarized descriptively by visit using summary statistics in addition to the above noted model.

The proportion of responders and non-responders for WOMAC pain, WOMAC physical function or users of rescue medication will be summarized by visit. Treatment comparisons will be made using a logit model with treatment effect as the only term in the model.

The pain intensity assessed on an 11-point NRS average and worst score between Baseline and each day will be tabulated by day and presented graphically.

A weekly average of all available pain scores will be calculated using the 11-point NRS average and worst score. MMRM model will be used to address the secondary objective to compare for change from baseline between treatment arms by weeks; and data will be presented graphically. The all available scores of daily NRS scores evaluated when the subjects replace the patch and the NRS scores evaluated before any rescue medication use will be analyzed.

The NRS pain score for assessment at Weeks 1, 2, 4, 8, and 12 is a mean of the NRS pain scores reported for pain over the last 24 hours for the 3 days (the last 2 days prior to each clinic visit and the day of the clinical visit) using the 11-point NRS average and worst score. MMRM model will be used to address the secondary objective to compare the change from baseline between treatment arms by weeks; and data will be presented graphically.

To address the objective for rescue medication, the proportion of subjects, the number of days using rescue and total rescue use during the entire treatment period will be summarized by treatment arms.

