Change from baseline in pain intensity will be tabulated on an 11-point NRS at Weeks 1, 2, 4, 8, and 12 (visits 4, 5, 6, 7, and 8) average and worst score between baseline and each week. The NRS pain score for assessment at Weeks 1, 2, 4, 8, and 12 (visits 4, 5, 6, 7, and 8) is the mean of the NRS pain scores reported for pain [REDACTED]

[REDACTED] using the 11-point NRS average pain intensity score and NRS worst pain intensity score. Baseline is [REDACTED]

Average pain intensity:

Noven Pharmaceuticals, Inc.

Protocol HP-5000-US-07

Statistical Analysis Plan

Page 34 of 58

Change from baseline in average pain intensity assessed on an 11-point NRS at Weeks 1, 2, 4, 8, and 12 (visits 4, 5, 6, 7, and 8) will be presented descriptively and analyzed similar to the primary analysis of the change from baseline as the repeated variable, with effects for treatment (HP-5000 and placebo), visit, treatment-by-visit interaction, and the baseline average pain intensity score as a covariate. With no adjustment for intercurrent events.

The average pain is collected through eDiary in clinic.

Worst pain intensity:

Change from baseline in worst pain intensity assessed on an 11-point NRS at Weeks 1, 2, 4, 8, and 12 (visits 4, 5, 6, 7, and 8) will be presented descriptively and analyzed similar to the primary analysis of the primary efficacy variable (refer to [Section 16.1.3](#)). A MMRM model will be used with change from baseline as the repeated variable, with effects for treatment (HP-5000 and placebo), visit, treatment-by-visit interaction, and the baseline worst pain intensity score as a covariate. With no adjustment for intercurrent events.

The worst pain is collected through eDiary in clinic.

A figure plotting the 3-day average of the average and worst NRS pain scores by visit will be generated.

16.3.6 CHANGE FROM BASELINE IN PAIN INTENSITY ASSESSED ON AN 11-POINT NRS OF A WEEKLY AVERAGE OF ALL AVAILABLE DAILY PAIN SCORES AT EACH WEEK FROM WEEK 1 THROUGH 12

Change from baseline to each week (Week 1 through 12) in pain intensity will be assessed on an 11-point NRS of a weekly average of all available daily pain scores at each week.

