All available scores of daily NRS scores evaluated when the subjects replace the patch and the NRS scores evaluated before any rescue medication use will be included. Weekly pain would be the mean of average NRS pain and mean of worst NRS pain over 7 days (e.g., Week 1 = average pain scores on Days 1 through 7). Baseline is defined 

A weekly average of all available daily pain scores will be calculated from subject's diaries. MMRM model will be used with change from baseline as the repeated variable, with effects for treatment (HP-5000 and placebo), visit, treatment-by-visit interaction, and the baseline 3-day average NRS score as a covariate. With no adjustment for intercurrent events.

A figure plotting the weekly average of the average and worst NRS pain scores by week will be generated.

Noven Pharmaceuticals, Inc.

Protocol HP-5000-US-07

16.3.7 CHANGE FROM BASELINE IN PATIENT GLOBAL ASSESSMENT (PGA) AT WEEKS 1, 2, 4, 8, AND 12

Subject's will be asked to complete the following statement: "How would you rate your osteoarthritis condition over the last 24 hours?" using a 5-point scale from 0 (Very Good) to 4 (Very Poor).

Change from baseline in PGA at Weeks 1, 2, 4, 8, and 12 (visits 4, 5, 6, 7, and 8) will be analyzed similar to the primary analyses (refer to [section 16.1.3](#)). An MMRM model will be used with change from baseline in PGA as the repeated dependent variable, with effects for treatment (HP-5000 and placebo), visit, treatment-by-visit interaction, and the baseline PGA score as a covariate. With no adjustment for intercurrent events. The observed value and change from baseline will also be summarized descriptively by visit using summary statistics in addition to the above noted model.

The responders are defined as subjects achieving a score of

0: Very Good or

1: Good

Non-responders are defined as subjects achieving a score of

2: Moderate or

3: Poor or

4: Very Poor

[figure not shown]
Subjects not assessed will be considered as having missing data.

The proportion of PGA responders and non-responders will be summarized by visit. Treatment comparisons will be made using a logit model adding PGA baseline as the covariate. This model will present an estimate of the odds ratio, Wald 95% CI, and p-value. The sample SAS code used for the Logit model for the PGA analysis can be found in [Appendix 2](#).

16.3.8 PATIENT GLOBAL IMPRESSION OF CHANGE (PGIC) AT WEEKS 1, 2, 4, 8, AND 12

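### For subjects who stop the patch but keep the eDiary, the plan sets no clear occasion for the daily NRS rating and does not clearly count it in the weekly NRS mean

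*SAP*

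**What the plan says.** **Which ratings enter the weekly mean.** SAP 16.3.6 names "All available scores of daily NRS scores evaluated when the subjects replace the patch and the NRS scores evaluated before any rescue medication use". Protocol 13.4.3.3 has nearly the same sentence: "The all available scores of daily NRS scores evaluated when the subjects replace the patch and the NRS scores evaluated before any rescue medication use". But SAP 16.3.6 also states, with no patch condition, that "A weekly average of all available daily pain scores will be calculated from subject's diaries", and its title calls the endpoint a "WEEKLY AVERAGE OF ALL AVAILABLE DAILY PAIN SCORES AT EACH WEEK". The model for this endpoint makes no adjustment for intercurrent events.

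**When ratings are made during treatment.** Protocol 10.1.3, at-home step 2b, reads "Perform and record scoring of the pain of the target knee using the NRS 11-point pain scale when subjects replace the patch". It adds an extra rating immediately before any rescue dose. The NRS section (10.3.1.4) gives the same two occasions.

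**What happens after the patch is stopped.** Protocol version 2.0, on which the SAP is based, keeps these subjects in the study (8.2.3). They are encouraged to "perform all procedures (including eDiary completion and blood draws) and follow the all requirements of the protocol (including the prohibited therapies), but without study treatment", through Week 13.

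**What the Screening Phase does.** Its at-home instructions tie the rating to the shower or bath, with a fallback: "Even if subjects do not take a shower or bath, the assessment is necessary every 24 hours". The treatment-phase NRS instruction has no such fallback. The no-shower note in protocol 9.2 is about replacing the patch, so it cannot apply to someone who no longer wears one.

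**The concern.** The retention rule and the NRS rules do not fit together. Subjects who stop treatment are to stay in the diary, and the analysis is meant to use what they record. But the regular rating is triggered by an act they no longer perform, and the inclusion sentence describes the regular rating by that same act.

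Read literally, a subject off the patch can supply only the rating made before rescue. A week without rescue is then missing and falls to the missing-at-random assumption of the model. A week with rescue is represented by the rescue days alone. Both differ from an average of all available daily scores in all randomised subjects.

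At stake is the weekly NRS endpoint. Onset may also be touched: SAP 16.3.13 defines it as the first significant NRS difference without saying which NRS series is used. Neither is in the fixed-sequence procedure.

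**Working it through.** The documents give no figure for this endpoint that could be reproduced, and the sample size and effect size are redacted. The check is a comparison of passages, a calendar count that needs no variance or stopping rate, and a range for size under stated assumptions.

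**1. Passages side by side, for a subject off the patch**

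| Rating | Occasion defined? | Named in the inclusion sentence? | An available daily score? |
|---|---|---|---|
| Regular daily rating | No | No | Yes, if recorded |
| Rating before rescue | Yes | Yes | Yes |

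The last two columns disagree in the first row, so SAP 16.3.6 supports two different data sets.

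**2. Days on which a pre-rescue rating is possible (literal reading)**

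Inputs: Week w covers Days 7w−6 to 7w (SAP 16.3.6: Week 1 is Days 1 to 7). Visits 4 to 8 fall on Days 7, 14, 28, 56 and 84. Rescue is prohibited from Visit 3 to Visit 4, on the two days before Visits 5 to 8, and on visit days (protocol 9.11).

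- Week 1, Days 1–7: all prohibited, 7 − 7 = **0 of 7**.
- Week 2, Days 8–14: Days 12, 13 and 14 prohibited, 7 − 3 = **4 of 7**. Weeks 4, 8 and 12 are the same (Days 26–28, 54–56 and 82–84).
- Weeks 3, 5, 6, 7, 9, 10 and 11: **7 of 7**.

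This uses protocol day numbers and on-schedule visits. SAP 6.1 numbers the Baseline day as Day 1. If 16.3.6 means that numbering, each week starts one protocol day earlier. Week 1 is still 0; Week 2 (protocol Days 7–13; 7, 12 and 13 prohibited) is still 4; Weeks 4, 8 and 12 become 7 − 2 = 5; and Weeks 3, 5 and 9, which then begin on a visit day, become 7 − 1 = 6.

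**3. How often a whole week would be empty (assumed rescue rule)**

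Suppose rescue is taken on permitted days when pain exceeds the subject's own mean by 0.5 or 1 SD, with independent normal days. The chance of no rescue is 0.6915 or 0.8413 per day.

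- Seven permitted days: 0.6915⁷ = 8%; 0.8413⁷ = 30%.
- Four permitted days: 0.6915⁴ = 23%; 0.8413⁴ = 50%.
- Week 1: 100%.

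**4. Size of the selection effect (assumed)**

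Take seven independent normal daily scores, with rescue on the k worst days. A simulation of 400,000 subject-weeks puts the mean of those days above the seven-day mean by 1.352, 1.055, 0.821 and 0.616 within-subject SD for k = 1, 2, 3 and 4. With a day-to-day SD of 1.0 to 2.0 points, the range is 0.616 × 1.0 = 0.6 to 1.352 × 2.0 = 2.7 points per affected subject. This applies to weeks with seven permitted days. In visit weeks rescue can fall on only four days, so the shift is smaller. If rescue is unrelated to knee pain, it is 0.

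**5. Between-arm effect (assumed)**

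Distortion = (share off patch on HP-5000 − share on placebo) × shift, with the shift equal in both arms and a simple average over subjects:

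- equal shares: 0;
- 8% versus 15%, 2 points: (0.08 − 0.15) × 2 = −0.14;
- 15% versus 8%, 2 points: +0.14;
- 5% versus 20%, 2 points: (0.05 − 0.20) × 2 = −0.30.

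**The case against.** The strongest reply is that no exclusion is written. SAP 16.3.6 says the two kinds of rating will go in; it does not say that nothing else will. The sentence can be read as confirming that the extra pre-rescue rating counts alongside the regular one. Protocol 10.1.3 step 2 calls for daily entries, step 2a adds an entry before sleep, and sites re-instruct subjects who miss entries. On that view all that is missing is a time of day for the rating once there is no patch to replace.

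Much of this stands. A reader might infer that the endpoint counts only patch-replacement and pre-rescue ratings. The documents do not say that; it is one of two readings. Ratings up to the day of stopping count on either. But a general call for daily entries does not settle whether an off-patch rating is collected, or whether the programmer keeps it, and the two readings give different data.

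The reply is also right about the selection effect. The NRS item asks about the last 24 hours, not the moment before a tablet, and rescue is allowed for headache and fever. The upward shift is plausible, not established.

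**Conclusion.** The point holds as a mismatch between the retention rule and the NRS trigger and inclusion rules. It is confined to secondary NRS endpoints outside the fixed sequence. The firm part is the calendar count: on the literal reading, days off the patch in Week 1 contribute nothing, and Weeks 2, 4, 8 and 12 offer at most four possible days. That rests on compliance with the rescue restrictions, on-schedule visits and protocol day numbering. The effect is thus partly missing data and partly selection of rescue days.

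Three stronger conclusions are not supported:

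- **That the treatment comparison is biased in a known direction.** Stopping and rescue rates by arm are unknown. The distortion is zero with equal stopping and equal shift, and takes either sign otherwise; 0.14 points is an illustration.
- **That the visit NRS mean is inflated too.** Protocol 13.4.3.3 takes it over the visit day and the two days before, when rescue is prohibited. In compliant subjects it is exposed to missing ratings, not upward bias.
- **That the main efficacy conclusions are at risk.** The WOMAC scores are taken by clinic questionnaire, and the primary and key secondary tests do not depend on the diary NRS.

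**What to change.** - **Protocol 10.1.3 step 2b and 10.3.1.4:** add that subjects who have stopped study treatment record the daily NRS approximately every 24 hours, as in the Screening Phase.
- **SAP 16.3.6:** state that the regular daily rating is included whether or not a patch was replaced, so that the inclusion sentence agrees with the endpoint's title. The same edit could say how a regular and a pre-rescue rating on one day are combined, which is also left open.

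If collection is complete, make the SAP change alone, before unblinding. It settles which recorded ratings count but cannot recover ratings that were never prompted.

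The cost is one protocol sentence, one SAP phrase and reuse of the Screening Phase eDiary prompt. No treatment or rescue rule changes.

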16.3.9 TREATMENT RESPONSE: REDUCTION IN THE WOMAC LK3.1 OA INDEX (PAIN)

The number and percentage of subjects with reduction in the WOMAC pain score of $\geq 30\%$, $\geq 50\%$, $\geq 70\%$, and $\geq 90\%$ at Weeks 1, 2, 4, 8, and 12 (visits 4, 5, 6, 7, and 8) from baseline will be summarized by treatment groups.

The responders are defined as subjects with a reduction in the WOMAC pain score of $\geq 30\%$, $\geq 50\%$, $\geq 70\%$, and $\geq 90\%$, and non-responders are defined as subjects with a reduction in the WOMAC pain score of $< 30\%$, $< 50\%$, $< 70\%$, and $< 90\%$, respectively. Treatment comparisons will be made using a logit model with treatment effect as the only term in the model analyzing the proportion of WOMAC pain score responders. For each comparison, an estimate of the odds ratio, corresponding Wald 95% CI, and p-value will be presented.

Noven Pharmaceuticals, Inc.

Protocol HP-5000-US-07

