16.3.10 TREATMENT RESPONSE: REDUCTION IN THE WOMAC LK3.1 OA INDEX (PHYSICAL FUNCTION)

The number and percentage of subjects with reduction in the WOMAC physical function score of $\geq 30\%$, $\geq 50\%$, $\geq 70\%$, and $\geq 90\%$ at Weeks 1, 2, 4, 8, and 12 (visits 4, 5, 6, 7, and 8) from baseline will be summarized by treatment groups.

The responders are defined as subjects with a reduction in the WOMAC physical function score of $\geq 30\%$, $\geq 50\%$, $\geq 70\%$, and $\geq 90\%$, and non-responders are defined as subjects with a reduction in the WOMAC physical function score of $<30\%$, $<50\%$, $<70\%$, and $<90\%$, respectively. Treatment comparisons will be made using a logit model with treatment effect as the only term in the model analyzing the proportion of WOMAC physical function score responders. For each comparison, an estimate of the odds ratio, corresponding Wald 95% CI, and p-value will be presented.

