16.3.11 TREATMENT RESPONSE: REDUCTION IN THE WOMAC LK3.1 OA INDEX (STIFFNESS)

[figure not shown]
The number and percentage of subjects with reduction in the WOMAC stiffness score of $\geq 30\%$, $\geq 50\%$, $\geq 70\%$, and $\geq 90\%$ at Weeks 1, 2, 4, 8, and 12 (visit 4, 5, 6, 7, and 8) from baseline will be summarized in a table by treatment groups.

The responders are defined as subjects with a reduction in the WOMAC stiffness score of $\geq 30\%$, $\geq 50\%$, $\geq 70\%$, and $\geq 90\%$, and non-responders are defined as subjects with a reduction in the WOMAC stiffness score of $<30\%$, $<50\%$, $<70\%$, and $<90\%$, respectively. Treatment comparisons will be made using a logit model with treatment effect as the only term in the model analyzing the proportion of WOMAC stiffness score responders. For each comparison, an estimate of the odds ratio, corresponding Wald 95% CI, and p-value will be presented.

16.3.12 PROPORTION OF SUBJECTS, THE NUMBER OF DAYS, AND THE TOTAL NUMBER OF RESCUE MEDICATION**TABLETS USED DURING THE TREATMENT PHASE**

Proportion of subjects who used rescue medication at any time during the entire treatment period and descriptive statistics for the number of days these subjects used rescue medication and the total number of rescue medication tablets used during the treatment phase will be presented by treatment arm.

The number and percentage of subjects using rescue medication will be summarized by treatment and overall. A logit model will be used to compare treatment against placebo. This model will not contain any baseline covariates but will present an estimate of the odds ratio, Wald 95% confidence interval, and p-value for use of rescue medication. A by-subject listing of

Noven Pharmaceuticals, Inc.

Protocol HP-5000-US-07

Statistical Analysis Plan

Page 38 of 58

all efficacy assessments collected will be presented.

For number of days of rescue medication and number of tablets of rescue medication during the treatment phase, an independent two sample t-test will be used to compare treatment against placebo. An estimate of the difference, the 95% CI, and the p-value will be presented. If the normality assumption is not supported by the data, a Wilcoxon Rank Sum Test will be used.

16.3.13 THE ONSET OF THE EFFECT: PAIN INTENSITY ASSESSED ON AN 11-POINT NRS CHANGE FROM BASELINE

Onset of the effect of HP-5000 will be defined as the first significant difference in NRS pain reduction between HP-5000 vs Placebo.

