16.3.16 RESPONDERS AND NON-RESPONDERS ANALYSIS

The proportion of subjects who are responders for WOMAC pain score, WOMAC physical function score, stiffness score, composite score, NRS, and users of rescue medication will be based on $\geq X\%$ improvement from baseline^[6]. At each time point, subjects having $X\%$ or greater improvement from baseline in WOMAC pain score will be defined as “responders”. The percentage change from baseline is defined as $(\text{Value at Week } X - \text{Baseline value}) * 100 / (\text{Baseline value})$. In other words, the responder indicator will be set to 1 if the percentage change is less than or equal to $-X\%$ and set to 0 if the percentage change is greater than $-X\%$ or missing. The different levels of required percent improvement from baseline are $X=5\%$ to 100% with 5% increments. These different thresholds for improvement will be summarized by visit. Results will be reported by means of a graph with response threshold on the X-axis and proportion of subjects who are responders in each treatment group on the Y-axis, this figure will only be completed for the WOMAC pain score. Corresponding statistics will be presented in a summary table. The same statistics will be provided for WOMAC stiffness score, physical function score, and composite score.

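### Do the WOMAC responder odds ratios in SAP 16.3.9–16.3.11 rest on different subjects from the percentages reported beside them?

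*SAP*

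**What the plan says.** SAP 16.3.9 defines a responder by a pain reduction at or above 30, 50, 70 or 90%, and then: "non-responders are defined as subjects with a reduction in the WOMAC pain score of" less than the respective cut-off. SAP 16.3.10 ("non-responders are defined as subjects with a reduction in the WOMAC physical function score of") and 16.3.11 ("non-responders are defined as subjects with a reduction in the WOMAC stiffness score of") follow the same pattern. Each section then specifies a treatment-only model; for pain it is a "logit model with treatment effect as the only term in the model analyzing the proportion of WOMAC pain score responders", reported as an odds ratio with a Wald interval and p-value. None of the three says what happens to a subject without a score, and none cites 16.3.16.

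SAP 16.3.16 defines a 0/1 responder indicator. It is "set to 0 if the percentage change is greater than" minus X%, and the same clause adds the case where the percentage change is missing. X runs from 5 to 100% in steps of 5. On scope, the section says "These different thresholds for improvement will be summarized by visit", and, beyond pain, "The same statistics will be provided for WOMAC stiffness score, physical function score, and composite score".

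For PGA, SAP 16.3.7 uses the other convention: "Subjects not assessed will be considered as having missing data". SAP 16.3.8 does the same for PGIC.

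SAP 16.3 runs these analyses on the ITT set, and section 8 takes the analysis set as the default denominator for percentages. Section 7.3 sets a subscale to missing if any item is missing, and provides imputation only for sensitivity analyses of the primary and key secondary endpoints.

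**The concern.** The class definitions are not exhaustive: with no score there is no reduction, so the subject is neither a responder nor a non-responder. Software fitting a logit model omits records with a missing outcome, while section 8 would still count the subject in the denominator of the printed percentage. A reader could then see a responder rate and an odds ratio in one table that cannot be derived from each other.

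The choice can also move the estimate. If missing scores are more common in one arm, counting them as non-response shifts the odds ratio towards the arm with fewer missing scores. The SAP uses both conventions for different instruments, so two programmers might code the same 30% responder endpoint differently. At stake are the odds ratios and nominal p-values for a family of other secondary endpoints.

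**Working it through.** **Which rule applies.** The plan gives no figure for the responder endpoints, so there is nothing to reproduce. The first step is to set the provisions side by side.

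| Feature | SAP 16.3.9–16.3.11 | SAP 16.3.16 |
|---|---|---|
| Scores | pain, function, stiffness | the same three, plus others |
| Timing | Weeks 1, 2, 4, 8, 12 | each time point, by visit |
| Cut-offs | 30, 50, 70, 90% | 5 to 100% by 5, i.e. 20 levels, including all four |
| Missing change | not addressed | indicator = 0 |
| Output | percentages, logit model | summary table; graph for pain |

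A logit model needs a 0/1 variable, and 16.3.16 holds the only one defined anywhere in the SAP for percent reduction in WOMAC. Protocol 13.4.3.3 supplies the link. In one short paragraph it asks for the proportions of responders for WOMAC pain and function and of rescue medication users, by visit, and then for a treatment-only logit comparison. The opening of SAP 16.3.16 takes up the first half, including the rescue users, and adds stiffness. SAP 16.3.9–16.3.11 take up the second half. They are two halves of one analysis.

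Using the 16.3.16 indicator also makes the other provisions agree. Every ITT subject has a value, so the ITT set (16.3), the section 8 denominator and the model population coincide. The mismatch appears only if 16.3.16 is set aside.

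**What the literal reading would change.** The documents give no rates; every rate below is an assumption. Let r be the response rate among scored subjects and m the fraction missing.

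- Scored subjects only: OR = [rA/(1−rA)] / [rP/(1−rP)]
- ITT, missing = non-responder: q = r(1−m), OR = [qA/(1−qA)] / [qP/(1−qP)]

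With rA = 0.55 and rP = 0.45, the scored-only OR is (0.55/0.45)/(0.45/0.55) = 1.49, whatever the missingness. The ITT version gives:

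| Missing, active / placebo | qA | qP | OR |
|---|---|---|---|
| 10% / 10% | 0.495 | 0.405 | 1.44 |
| 15% / 15% | 0.4675 | 0.3825 | 1.42 |
| 20% / 20% | 0.440 | 0.360 | 1.40 |
| 10% / 13% | 0.495 | 0.3915 | 1.52 |
| 13% / 10% | 0.4785 | 0.405 | 1.35 |

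With 10% missing on active, the two versions agree at about 12.0% missing on placebo.

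A harsher case assumes 200 per arm and a 10-point imbalance:

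- 10% missing on active, 20% on placebo. Scored subjects: 99/180 vs 72/160, OR 1.49, p = 0.066. ITT: 99/200 vs 72/200, OR = (99×128)/(72×101) = 1.74, p = 0.0065.
- The reverse. Scored subjects: 88/160 vs 81/180, OR 1.49, p = 0.066. ITT: 88/200 vs 81/200, OR = (88×119)/(81×112) = 1.15, p = 0.48.

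With complete data the two codings are identical.

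**The case for a change.** The best case for a change is that the link to 16.3.16 has to be inferred. That section describes a table and a graph and names no model, and neither place cites the other. The two responder sections just before 16.3.9, for PGA and PGIC, adopt the opposite convention. Section 7.3 does not extend imputation to these endpoints, and protocol 13.4.3.3 gives no missing-score rule. The sample logistic code in SAP Appendix 2, written for PGA, filters on visit and has no step that gives a value to an absent record. The harsher illustration shows that a nominal p-value can cross 0.05.

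Some of this stands. The pointer is missing, and a coding rule is best settled before unblinding. It does not follow that the rule is open. The PGA and PGIC text points the other way: where the authors want unassessed subjects left out, they say so, and they do not say so for WOMAC. The sample code takes a response variable as given and is silent on how it is derived. The table shells issued with the SAP would show the layout, but they are not in the public file, and their absence is not evidence of a gap. The large swings need one arm to have twice the other's missing fraction.

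The 16.3.16 rule has a cost: through section 7.3, a single missing item counts as non-response. That is a fair trade for one denominator throughout.

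**Conclusion.** No change follows. SAP 16.3.9–16.3.11 leave out a detail that 16.3.16 supplies for the same scores, visits and cut-offs, and an analyst who codes the models with that indicator gets rates and odds ratios on the same ITT subjects. A cross-reference would record a rule the SAP already contains; it would not alter an analysis.

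This rests on reading 16.3.16 as governing, which the protocol paragraph and the section 8 denominator support. If an analyst nevertheless modelled scored subjects only, the assumed 55% against 45% example gives 1.49 in place of 1.35 to 1.52 for missingness of 10 to 20% with at most a 3-point imbalance. The actual size and direction cannot be known from the documents. In either case the effect is confined to other secondary endpoints, which protocol 13.4.3.2 keeps out of the fixed sequence. The primary and key secondary conclusions are untouched.
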